### Analysis

If more than 5% of the participants are not radiologically confirmed CAP, then we will perform a sensitivity analysis using participants only with the radiologically confirmed CAP cases.

A second model will be developed excluding immunocompromised persons to evaluate PCV13 VE without those who may not be able to respond to the vaccine.

## 6.1.1.2. Primary Endpoint 1- Sensitivity Analyses

Several sensitivity analyses will be performed for estimating the VE against PCV13 VT serotype as well as against PPV23 VT serotype S. pneumoniae.

#### Selection of controls using propensity score matching

In the 1st sensitivity analysis, the cases will be the patients with CAP in whom PCV13 serotypes are identified by any method and the controls will be the patients with CAP without having VT serotype (even the CAPs for which the serotype was not identified). The controls will be selected using propensity score matching. A propensity score is the conditional probability of assignment to a treatment given a vector of covariates including the values of all treatment confounders (vida infra). We will select the required number of controls matching by the propensity score of the case. Several types of propensity score matching are available in literature. We will use nearest neighbor matching (without replacement, meaning a control cannot be the control of any other case) within a specified caliper distance (Rosenbaum & Rubin, 1985). The caliper distance will be set to 0.2 of propensity score (i.e., 0.2 standard deviations of whatever distance will be measured), so that matching controls remain within the specified distance of the propensity score. Note that 0.2 of the pooled standard deviation of the logit of the propensity score will eliminate approximately 99% of the bias due to the measured confounders (Austin 2011). The maximum number of controls for a case will be determined based on the exact case-control ratio in the data. If less than the maximum number of controls exists within the set caliper distance of 0.2, then only those controls within the caliper distance will be selected and that case will have less than the maximum number of controls.

DMB02-GSOP-RF02 5.0 Statistical Analysis Plan Template 05-Dec-2019
PFIZER CONFIDENTIAL
Page 32
TMF Doc ID: 98.03

We may also perform a sensitivity analysis by selecting controls setting the caliper distance to 0.1 of the propensity score.

## Variables to be used to calculate the propensity scores

Variables for calculating the propensity score.

- Patients' age: continuous
- Sex: female=0, male=1
- Nationality: Spanish=0, non-Spanish=1
- Risk level: low-risk=0, at-risk=1, high-risk=2
- PSI score: continuous
- Antibiotic use within past 14 days: no=0, yes=1)
- Influenza vaccination within past one year: yes=0, no=1
- Pneumonia in the last year: ordinal value=0, 1,2,3
- Season of admission: Spring (Mar-May)=0, Summer (Jun-Aug)=1, Autumn (sep-Nov)=2, Winter (Dec-Feb)=3.
- PPV23 receipt in past 5 years: yes=0, no=1
- CAP event occurrence during COVID-19 pandemic: 0=not during COVID-19, 1=During COVID-19 (The study is started in the pandemic period; the variable will be used if we find a non-pandemic period during the study period)

The study site will be exactly matched. Note that the categorical variable will be put in the model like the ordinal values.

The conditional logistic regression will be employed to estimate odds of exposure to PCV13 among these matched cases and controls. The VE estimate will be calculated as  $(1 - \text{odds ratio}) \times 100\%$ . We will use a two-sided alpha of 0.05 for all analyses.

In the 2nd sensitivity analysis (PPV23 Naïve population), the cases will be the hospitalized CAP in whom PCV13 serotypes are identified by any method and had not received PPV23 in the last five years from the date of visit; the controls (also PPV23 Naïve population), will be selected using the propensity score matching as described above. A conditional logistic regression will be employed to estimate odds of exposure to PCV13 among cases versus controls in the PPV23 naïve population. The VE estimate will be calculated as (1 – odds ratio) × 100%. We will use a two-sided alpha of 0.05 for all analyses.

In the 3rd sensitivity analysis (Suzuki Method), cases are the hospitalized patients with CAP in whom VT serotypes are identified by any method including UADs, routine culture of blood, pleural fluid, or other high-quality respiratory tract specimen, and the controls are the patients in whom pneumococcus is not detected by any method (culture, UAD, or Binax), similar to a recently published article (Suzuki et al, 2017). The controls will be selected using the propensity score matching as described above. A conditional logistic regression will be employed to estimate odds of exposure to PCV13 among cases versus controls. The VE estimate will be calculated as (1 – odds ratio) × 100%. We will use a two-sided alpha of 0.05 for all analyses.

DMB02-GSOP-RF02 5.0 Statistical Analysis Plan Template 05-Dec-2019
PFIZER CONFIDENTIAL
Page 33
TMF Doc ID: 98.03

In the 4th sensitivity analysis (Broome/Indirect cohort method), cases are the patients with CAP in whom VT serotypes are identified by any method including UADs, routine culture of blood, pleural fluid, or other high-quality respiratory tract specimen, and the controls are the patients having a NVT pneumococcal CAP, i.e. the patients in whom pneumococcus is detected from blood/pleural/high-quality sputum culture, Binax or UAD1/2 positive, and VT serotypes are not identified from culture or UAD1/2. The controls will be selected using the propensity score matching as described above. A conditional logistic regression will be employed to estimate odds of exposure to PCV13 among cases versus controls. The VE estimate will be calculated as (1 – odds ratio) × 100%. We will use a two-sided alpha of 0.05 for all analyses.

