For the primary endpoint, the cases will be the patients with CAP in whom PCV13 serotypes are identified by any method and the controls will be the patients with CAP without having VT serotype (even the CAPs for which the serotype was not identified). Multivariable logistic regression model (Appendix 3.3), will be applied to estimate odds of exposure to PCV13 among cases versus controls. All VE estimates will be calculated as  $(1 - \text{odds ratio}) \times 100\%$ . Both unadjusted and adjusted VE will be estimated. Patients' age, sex, study site and the variables deemed to be potential confounders on the basis of prior knowledge (e.g. nationality to be modeled as Spanish vs. non-Spanish; risk level to be modeled as low vs. at-risk vs. high-risk; BMI category to be modeled as obese vs. overweight vs. normal vs. underweight; PSI score as continuous; current drug abuse; antibiotic use within past 14 days; influenza vaccination within the last year; pneumonia in last year [ordinal variable, 0,1,2,3] and PPV23 receipt in past 5 years) will be included in the multivariable regression model for adjustment. Initially, we will employ bivariate models, and only the variables significant at p<.20 in the bivariate models will be included in the final model for adjustment.

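### The propensity model scores season of admission 0 to 3 as if it were ordinal, leaving a winter/spring pattern unadjusted in the matched analyses; the primary model names no season or calendar term

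*SAP*

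**What the plan says.** The propensity variable list in SAP 6.1.1.2 gives "Season of admission: Spring (Mar-May)=0, Summer (Jun-Aug)=1, Autumn (sep-Nov)=2, Winter (Dec-Feb)=3" and "Risk level: low-risk=0, at-risk=1, high-risk=2". Below the list it states: "Note that the categorical variable will be put in the model like the ordinal values".

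This score selects controls for sensitivity analyses 1 to 4, which SAP 6.1.1.2 introduces with: "Several sensitivity analyses will be performed for estimating the VE against PCV13 VT serotype as well as against PPV23 VT serotype S. pneumoniae". Propensity-matched sets are used again in the PPV23–PCV13 test (SAP 6.3.2.1) and the COVID-19 effectiveness models (SAP 6.3.7.1).

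The main analysis (SAP 6.1.1.1) is different. An unmatched multivariable logistic regression "will be applied to estimate odds of exposure to PCV13 among cases versus controls". Its covariates open with "Patients' age, sex, study site and the variables deemed to be potential confounders on the basis of prior knowledge (e.g. nationality" and close with "PPV23 receipt in past 5 years) will be included in the multivariable regression model for adjustment". Risk level is categorical there: "risk level to be modeled as low vs. at-risk vs. high-risk". Neither season nor calendar time is named, but the list is given as examples.

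**The concern.** Season has no first and last level. A 0–3 score can represent only a steady change from spring through to winter. It cannot represent the cold half of the year differing from the warm half, which is an obvious pattern to allow for in pneumonia.

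Risk level is ordered, so a score is less objectionable. It is still the confounder for which matching was brought in: Protocol Section 3 describes PCV13 recipients as enriched for risk factors, and Protocol 12.4.1 justifies the matched analysis by the risk-based catch-up policy. A check on the primary result should not handle that variable more crudely than the primary model does.

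A mis-specified score is also unlikely to be noticed. SAP 6.1.1.2 relies on the caliper to remove nearly all bias from measured confounders, which presumes an adequate score, and it specifies no balance check after matching.

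Finally, the SAP treats season as a confounder in the propensity list but does not name it in the primary model. Protocol Section 7 puts PCV13 coverage at around 8% in September 2019 and expects it to increase, while enrolment runs for about four years.

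**Working it through.** **1. The plan's own figure.** The documents give no number for this modelling choice. The base-case sample size only sets the scale. With 15% coverage in controls and OR 0.40, coverage in cases is 0.40×0.15/(0.85+0.40×0.15) = 0.0659. Two-sided alpha 0.025, 80% power, a ratio of 1692/170 and the Fleiss continuity correction give 170 cases and 1,692 controls, as stated.

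**2. What a linear season score can see.** Let winter and spring be 1 and summer and autumn 0, on scores 0 (spring), 1, 2, 3 (winter). With equal season shares the mean score is 1.5 and the slope numerator is (−1.5)(1)+(−0.5)(0)+(0.5)(0)+(1.5)(1) = 0, so the fitted slope is exactly zero. With assumed shares of 25/15/22/38% the mean score is 1.73, the covariance is 0.25×(−1.73)+0.38×1.27 = 0.050, and the score variance is 1.457. The slope is 0.034 per step. The share of the pattern's variance captured is 0.050²/(1.457×0.63×0.37), about 0.7%.

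**3. The same check for risk level.** The shares are 20/44/36%; the 36% immunocompromised is from Protocol 12.1.2 and the rest is assumed. For a step (0,1,1) the covariance is 0.232, the score variance 0.534 and the pattern variance 0.16, so the line captures 0.232²/(0.534×0.16) = 63%. For a non-monotone pattern on the log-odds scale (0, ln 3, ln 1.5) the covariance is 0.0453 and the pattern variance 0.194, so it captures about 2%.

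**4. Effect on VE.** Large simulated data were used (1.5 million patients, true VE 60%, baseline coverage 15%, baseline VT share 9%). Stratification on 200 propensity strata with Mantel-Haenszel pooling stood in for matching. All season and risk associations are assumptions. Correctly specified models returned 59.6 to 60.6, which shows the simulation noise.

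| Assumed pattern | Score: linear | Score: indicators | Regression, risk in 3 categories, no season |
|---|---|---|---|
| Season unrelated to PCV13 status | 59.9 | 59.9 | 59.9 |
| Season, mild effects | 60.2 | 60.4 | 60.0 |
| Winter/spring high: OR 1.3 vs 0.77 on vaccination, 1.5 vs 0.67 on VT | 56.5 | 60.1 | 56.5 |
| Same, stronger: 1.7 vs 0.6 on both | 51.3 | 59.6 | 51.3 |
| Risk step, vaccination OR 2 | 60.0 | 60.1 | 60.2 |
| Risk step, vaccination OR 3 | 59.7 | 60.6 | 60.6 |
| Risk non-monotone: vaccination OR 1, 3, 1.5; VT OR 1, 2, 1.2 | 54.4 | 59.8 | 59.8 |

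Under a winter/spring pattern the linear score gives the same answer as leaving season out.

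**5. Calendar time left out.** Assume four equal years, control coverage rising evenly from 10% to 20%, and OR 0.40 in every year. Pooling the expected cells gives a VE of 57.6% if VT share rises from 7% to 11%, and 61.8% if it falls from 11% to 7%. The direction is not fixed.

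**6. Scale against sampling error.** Expected cells are 11.2 and 158.8 cases (vaccinated, unvaccinated) and 253.8 and 1,438.2 controls. SE(log OR) = √(1/11.2+1/158.8+1/253.8+1/1438.2) = 0.32, and the 95% interval around 60% is about 26% to 78%. The shift to 56.5% is ln(0.435/0.40) = 0.084, or 0.27 SE. The shift to 51.3% is ln(0.487/0.40) = 0.197, or 0.62 SE.

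**7. Room in the primary model.** With three sites, the named covariates use 16 parameters: age 1, sex 1, site 2, nationality 1, risk 2, BMI 3, PSI 1, drug abuse 1, antibiotics 1, influenza vaccine 1, prior pneumonia 1, PPV23 1. The ten-events rule in SAP Appendix 3.3 allows 170/10 = 17. Season-by-year cells would add 4×4−1 = 15, three season indicators 3, and a calendar-year slope or a two-level season contrast 1.

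**The case against.** The strongest reply is that season has not been shown to confound anything. Exposure is PCV13 receipt at any time within ten years (SAP 6.1.1.1), with vaccination in the last 30 days excluded (Protocol 12.1.3.1). Giving doses during influenza campaigns fixes when people are vaccinated; it does not show that patients admitted in different seasons differ in cumulative coverage. No section gives coverage or VT share by season. This stands as a limit on size. It does not justify the coding, since the SAP itself chose season as a matching variable.

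A reader might infer that risk level, too, is poorly controlled throughout. The documents do not support that. The primary model uses three categories. High-risk is the immunocompromised group (SAP Appendix 2.4), so in immunocompetent analyses only two levels remain and a 0/1 score is the same as an indicator. A true step costs about 1 VE point or less; only a non-monotone pattern cost about 5.

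A reader might also infer that the primary model excludes season. The list is illustrative, so season is unnamed, not ruled out. The propensity list also carries a pandemic-period flag, although it is binary and conditional.

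Lastly, the matched analyses are secondary and the shifts are well under one standard error. That is fair, but a bias check that cannot detect the pattern in question gives false reassurance whatever the interval width.

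**Conclusion.** The point holds in a limited form. Ordinal scoring of season is a stated mis-specification of the score used in sensitivity analyses 1 to 4, the PPV23–PCV13 test and the COVID-19 models. Ordinal scoring of risk level is an inconsistency with the primary model, confined to matched analyses that include immunocompromised patients. Not naming season or calendar time in the primary model is a gap, given that the SAP lists season as a matching variable and coverage is expected to rise.

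The documents do not fix the size. Against a true VE of 60%, the bias is nil if season is unrelated to PCV13 status, at most about half a point with mild effects, 3.5 points with an aligned winter/spring pattern and 8.7 points in the strong version. Omitted calendar time moved VE by about 2 points in either direction. Every one of these rests on assumed associations, and stratification replaced the planned matching. They support a change of specification; they do not support a claim that the primary estimate is materially biased.

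**What to change.** In SAP 6.1.1.2, delete the sentence on ordinal values and enter season (three indicators) and risk level (two indicators) as categorical terms in the propensity model.

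In SAP 6.1.1.1, name one parsimonious season or calendar-year term and keep it regardless of the p<.20 screen. SAP Appendix 3.3 states p<0.10 instead, so the two thresholds need reconciling, and the exemption should be written in both places. Full season-by-year cells are not advised: with the 16 parameters already named they would reach 31, against 17 allowed at 170 cases. A calendar-year slope or a two-level season contrast fits exactly (17); three season indicators (19) fit only if the screen drops other terms or more cases accrue.

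The cost is SAP wording, a class declaration in the program, three extra degrees of freedom in the propensity model (two for season, one for risk level) and one to three in the primary model. No sample-size figure changes.

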## Adjustment of Bias in the Indirect Cohort (Broome Method)

Since the Broome method is subject to bias caused by PCV13 vaccination increasing the chance of NVT carriage in vaccinated compared to unvaccinated individuals, through reduction in VT carriage and replacement by NVT carriage (Andrews et al, 2011), we will pursue adjustment for the bias due to carriage replacement using the following formula if pneumococcal colonization data is available for the UAD control population:

$$VE_{Broome} = 1 - \frac{1 - VE}{P_{n|v} + P_{n|u}}$$
 equation (1)

where,  $VE_{Broome}$  is observed VE by the indirect cohort method,  $P_{n|u}$  is the probability of NVT carriage in an unvaccinated individuals;  $P_{n|v}$  is the probability of NVT carriage in a vaccinated individuals.

If we assume complete serotype replacement at any point in time, i.e. overall carriage rates remain stable and equal in vaccinated and unvaccinated individuals then the equation (1) becomes:

$$VE_{Broome} = 1 - \frac{1 - VE}{1 + VE_c P_u \div (1 - P_u)}$$
 equation (1)

where, VEc is VE against carriage,  $P_u$  is the proportion of carriage that is VT in the unvaccinated group. This formula will be used along with estimates for  $VE_c$  and  $P_u$  to assess the possible bias in estimating VE.

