An interim analysis is planned after accrual of 170 VT-cases but depending on the VE point estimate, the proportion of CAP cases that are vaccine serotype, and the frequency of PCV-13 vaccination in the study population, additional subjects may be needed to allow for adequate statistical power. On this basis, approximately 4 years of enrolment is planned.

If the anticipated PCV20 is approved during the enrolment of cases for VE analysis as expected (projected to be in use no sooner than late 2022), subjects with PCV20 exposure will be excluded from the cases and the controls for the PCV13 VE analysis. Initial PVC20 use is expected to primarily involve those aging into the over 60 age group, and substantial number of persons with a history of PCV13 vaccination are expected to remain in that age group population.

Laboratory testing. The Central laboratory will conduct BinaxNOW[®] (Alere, Walthman, MA) and the serotype-specific UAD1 and 2 assays (Pfizer, Inc) to test urine samples from all enrolled participants as the study-related procedures. Results from SOC tests performed on enrolled subjects will be also collected, including respiratory, blood, and pleural fluid cultures and urine pneumococcal antigen testing. All pneumococcal isolates will undergo serotyping.

Pneumococcal Carriage and RSV infection assessments. In addition, patients at selected study sites will provide a saliva sample to test for pneumococcal carriage and RSV infection but, if they decline this procedure at the time of collection, they will not be excluded from the study. Samples will be processed for pneumococcal detection by the standard, conventional culture diagnostic approach and molecular methods. RSV will be detected by molecular methods only.

Incidence assessment. Population-based incidence of CAP will also be estimated in this study. Nearly all CAP hospitalisations in the surveillance regions are expected to involve the study hospitals. Every effort will be taken to identify all pneumonia patients admitted to

PFIZER CONFIDENTIAL CT45-GSOP-RF152.0 Low-Interventional Study Protocol Template 05-Dec-2019 Page 30 of 70

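### SAP 6.1.1.2: as the text reads, the first Broome bias equation uses the sum of the two NVT carriage probabilities, but the second equation follows only from their ratio, and both are numbered (1)

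*SAP*

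**What the plan says.** The 4th sensitivity analysis in SAP 6.1.1.2 compares VT cases with NVT pneumococcal controls. The SAP then notes that this estimate is biased, because PCV13 can raise NVT carriage in vaccinated people. It plans "adjustment for the bias due to carriage replacement using the following formula if pneumococcal colonization data is available for the UAD control population".

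Two equations follow, both labelled equation (1):

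- First: `VE_Broome = 1 - (1 - VE) / (P_n|v + P_n|u)`. Here P_n|v "is the probability of NVT carriage in a vaccinated individuals" and P_n|u "is the probability of NVT carriage in an unvaccinated individuals".
- Second, introduced with the assumption that "overall carriage rates remain stable and equal in vaccinated and unvaccinated individuals then the equation (1) becomes": `VE_Broome = 1 - (1 - VE) / (1 + VE_c × P_u ÷ (1 - P_u))`. Here VE_c "is VE against carriage" and P_u "is the proportion of carriage that is VT in the unvaccinated group".

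The closing sentence says that the formula will be combined with estimates of VE_c and P_u "to assess the possible bias in estimating VE". Neither document gives a value for any of these quantities.

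**The concern.** The second equation is presented as a special case of the first, but a sum of two probabilities does not reduce to it. The opening sentence points to the formula that comes next, which is the one with the sum. Because both carry the same number, an analyst holding carriage data by vaccination status could reasonably program the first. Both equations also express the observed Broome VE in terms of the true VE. A correction needs the inverse, and the SAP does not write it out.

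At stake is the adjusted result of a sensitivity analysis whose bias the SAP itself describes. At low or moderate carriage, the sum would move VE upward, whereas the bias described calls for a downward correction. The result would still lie in a believable range.

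**Working it through.** **Step 1. Reproduce the SAP's second denominator.** Let C be total carriage, equal in both groups under complete replacement.

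- Unvaccinated: `P_n|u = C(1 - P_u)`.
- Vaccinated: VT carriage falls to `C × P_u × (1 - VE_c)` and NVT fills the gap, so `P_n|v = C - C × P_u × (1 - VE_c) = C(1 - P_u + VE_c × P_u)`.
- Ratio: `P_n|v / P_n|u = 1 + VE_c × P_u / (1 - P_u)`. This is exactly the second denominator, and C cancels.
- Sum: `P_n|v + P_n|u = C[2(1 - P_u) + VE_c × P_u]`. This still depends on C and does not give the second denominator.

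**Step 2. Limiting check.** If vaccination does not change NVT carriage (both probabilities equal p), there is no replacement bias and VE_Broome should equal VE. The ratio is then 1, as required. The sum is 2p, which equals 1 only when p = 0.5.

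**Step 3. Effect on a corrected estimate.** Inverting gives `VE = 1 - (1 - VE_Broome) × D`, where D is the denominator. For illustration, the observed Broome VE is set to 60%, the planning VE in SAP 2.2. All carriage values below are assumptions.

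| NVT carriage, vaccinated / unvaccinated | Ratio | VE by ratio | Sum | VE by sum |
|---|---|---|---|---|
| 10% / 9% | 1.111 | 55.6% | 0.19 | 92.4% |
| 6% / 5% | 1.200 | 52.0% | 0.11 | 95.6% |
| 20% / 17% | 1.176 | 52.9% | 0.37 | 85.2% |
| 8.5% / 7.0% (C = 10%, P_u = 0.3, VE_c = 0.5) | 1.214 | 51.4% | 0.155 | 93.8% |
| 76% / 72% (C = 80%, P_u = 0.1, VE_c = 0.5) | 1.056 | 57.8% | 1.48 | 40.8% |

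First row in full: 1 - 0.40 × (0.10/0.09) = 0.556, and 1 - 0.40 × (0.10 + 0.09) = 0.924. In the fourth row, the SAP's second equation gives D = 1 + 0.5 × 0.3/0.7 = 1.214 and VE = 51.4%, the same as the ratio.

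**Step 4. Range.** For P_u from 0.1 to 0.5 and VE_c from 0.3 to 0.7, the ratio gives 32% to 59% whatever the value of C. The sum gives about 92% to 95% at C = 10%, 85% to 91% at C = 20%, 78% to 86% at C = 30% and 63% to 77% at C = 50%.

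The error changes direction when the sum exceeds the ratio, that is when C exceeds `ratio / [2(1 - P_u) + VE_c × P_u]`. With VE_c = 0.5:

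- P_u = 0.1: 1.056/1.85 = 0.57.
- P_u = 0.3: 1.214/1.55 = 0.78.
- P_u = 0.5: 1.5/1.25 = 1.2, which C cannot reach.

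**The case against.** **The plus sign may not be the author's.** The next equation has a division sign inside its denominator. A division sign in the first equation would make the derivation exact and could have been misread as a plus in the PDF text. This stands, and it is why the source file must be checked first. If the sign is a division, the contradiction disappears. The duplicate number, the unclear reference in the closing sentence and the missing inverted form remain as editorial matters.

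**The formula tied to inputs is the right one.** VE_c and P_u appear only in the second equation, so an analyst who follows the closing sentence gets the correct result. This also stands. A reader might infer that the corrected VE would be grossly overstated in any case. The documents do not support that: the first equation would have to be the one applied, and the size and direction of the error depend on carriage values they do not give. If the two probabilities were read as shares among carriers (C = 1), P_u = 0.3 and VE_c = 0.5 would give 38.0% by the sum against 51.4% by the ratio, an understatement. That reading fits poorly with the SAP, which defines them as probabilities in individuals, but it shows that overstatement is not general.

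**The adjustment may never run.** A reader might infer a second defect, because neither document enrols a UAD control population. In this study "patients at selected study sites will provide a saliva sample to test for pneumococcal carriage and RSV infection", and all of these are CAP patients. But SAP 6.3.4.1 lists UAD control subjects among other, outside sources, and the adjustment here is expressly conditional on such data being available. Not running it is an outcome that the plan allows, so no change of carriage source is called for.

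**Little depends on it.** The adjustment belongs to one of several sensitivity analyses. The primary VE comes from the multivariable logistic regression in SAP 6.1.1.1 and does not use it. This is correct and limits the weight of the point.

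**Conclusion.** As the text reads, the two equations contradict each other: under the SAP's own complete-replacement assumption, the second follows from the ratio and cannot follow from the sum. The second equation is correct under that assumption.

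Harm arises only if the plus sign is genuine and the first equation is applied directly to carriage data, which the opening sentence permits. In the 10% / 9% example the adjusted VE would then be 36.8 percentage points too high (92.4% - 55.6%). That figure rests on an assumed observed Broome VE of 60% and assumed carriage. The error shrinks as carriage rises and can reverse at very high carriage. Its reach is the conditional adjustment of the 4th sensitivity analysis and nothing else.

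**What to change.** 1. Confirm the operator in the SAP source file.
2. If it is a plus sign, replace the first denominator with `P_n|v / P_n|u`.
3. Number the general equation (1) and the complete-replacement form (2). Say that (1) takes NVT carriage by vaccination status and (2) takes estimates of VE_c and P_u, and name the intended equation in the closing sentence.
4. State the form to be programmed: `VE = 1 - (1 - VE_Broome) × (P_n|v / P_n|u)`. Under complete replacement, `1 + VE_c × P_u / (1 - P_u)` takes the place of the ratio.

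If the source file already shows a division sign, only items 3 and 4 remain. The cost is a few lines of SAP wording. Data collection, sample size and the primary analysis do not change.
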